4.3 Objectives

The project emphasizes evaluation of the clinical utility of pharmacotherapy with Vivitrol (VI) or Vivitrol + PN (PNV) in comparison to a drug education (DE) condition. Descriptive statistics will provide an overall assessment of the implementation of the protocol. The aims of this project include:

Aim 1: Assess the feasibility and clinical utility of a 24-week protocol of long-acting naltrexone (by intramuscular *injection*; VI) provided with and without a PN component (VI, PNV). Measures include side effects, adverse events, retention, and acceptance of the procedures by participants and clinicians. Acceptance will also be assessed among correctional staff.

Aim 2: Examine the effectiveness of Vivitrol provided with and without a PN component (VI, PNV) for its ability to prevent relapse to illicit opioid use, reduce drug-related criminal activity, curtail engagement in HIV-risk behaviors, and increase employment compared to a group receiving only drug education (DE) to assist in relapse prevention after release from jail. The VI and PNV groups will receive VI monthly for the entire 6-month intervention phase. Th PNV group will be provided with PN for 3 months to provide assistance in accessing community treatment after release from jail. Primary measures include DSM-5 diagnosis at time to relapse (defined as self-report of daily opioid use for one week), protocol adherence, and opioid-negative urine samples during the study.

Aim 3: Collect cost data using the Drug Abuse Treatment Cost Analysis Program (DATCAP) and estimate savings from reduced drug use, reduced criminal activity and re-incarceration, and increased employment. Data will support benefit-cost and cost-effectiveness analyses of depot pharmacotherapy with Vivitrol for released offenders with opioid use disorders.

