6.2 Secondary Outcome Measures

- HIV risk behaviors (compared using repeated measures procedures to evaluate possible change in sexual and drug-related behaviors that may inhibit or promote HIV infection) measured by the HIV-GAIN;
- (2) Self-reported number of days incarcerated during the intervention and follow-up phases;
- (3) Self-reported number of days of opioid and other drug use measured by TLFB, and objective measures of drug use by urine drug screens (UDS) at the 6-month post-release assessment (end of the intervention phase);
- (4) Self-reported days in drug abuse treatment;
- (5) Self-reported number of arrests;
- (6) Self-reported craving for opioids;
- (7) Self-reported number of overdoses; and
- (8) Self-reported motivation for treatment.

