8.0 STUDY ASSESSMENTS

Measures and instruments will be used to ensure a comprehensive assessment of status and functioning variables. These data, along with the DATCAP, will also be used to support the economic analysis. (The DATCAP will be administered during Year 2.) On average, screening and eligibility assessments will be completed in 4-6 hours (specific to treatment group). Post-release assessments will be completed in approximately 30-60 minutes. Medication Management visits are expected to take approximately 30-60 minutes.

Timepoints	Screening	Pre-	Post-release	
_		release		
Clinic Visits			Medical Mgmt	Assessments
				Months 1, 3,
				6, 7, 12
Measures				
Safety & Med. Measures				
Physical Exam / Med History	Х			
Injection site inspection	Х		X	
Vitals	Х		X	
12-lead ECG	Х			
Clinical Lab Tests	Х			
HIV Test	Х			
Pregnancy Test	Х		X	
Prior/Concomitant Meds	Х		X	
AEs			X	Х
Drug Use Measures				
DSM-5 Checklist	Х			
COWS (Withdrawal)	Х			
SOWS (Withdrawal)	Х			
Urine Drug Screen (UDS)	Х	Х	X	Х
Substance Use Report (TLFB)	Х	Х	X	Х
VAS (Craving)	Х	X	X	X
Crime and Recidivism				
Self-Report Arrest/Tx History			X	Х
Arrest Records				Х
CJ-DATS Crime Grid	Х			
HIV Risk Measure				
HIV-GAIN	Х			X
Cost				
Form 90				

Table	1. Data	Collection	Time and	Event	Schedule
I UDIC	I. Dutu	00110011011	This and		ouncaute

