8.3.2 CJ-DATS Crime Grid

Criminal Justice history will be documented including information about criminal activity, arrests, convictions, and incarcerations with this 24-item section of the CJ-DATS intake instrument.

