10.4.3 Economic Analysis (Aim 3)

The costs of the Vivitrol will be estimated using the Drug Abuse Treatment Cost Analysis Program (DATCAP_[d1]; French, 2003b). The DATCAP is a data collection instrument and interview guide designed to estimate the costs of substance abuse treatment and related interventions. Because the DATCAP organizes cost data across standard categories of resources (e.g., personnel, buildings and facilities, supplies and materials, and miscellaneous), it can be used for other types of interventions including pharmacotherapies. Cost data will be obtained to calculate the total annual cost of Vivitrol and the average per-client cost. We will not include any costs specific to research conducted under this study. To ascertain the full economic impact of Vivitrol, cost data will be compared to changes in key clinical measures of effectiveness (e.g., time to relapse, days of abstinence, re-arrest) to estimate cost-effectiveness ratios. Cost-effectiveness analysis (CEA) is inherently an incremental analysis that compares doing a little more or a little less of something to capture marginal variations in costs and effectiveness across interventions (Gold et al., 1996). Differences in program cost are divided by differences in program effectiveness to calculate incremental cost-effectiveness ratios (ICERs). One can then compare the ratios of cost to outcome for two or more alternative programs (in this case Vivitrol) to determine which programs are relatively more cost-effective (i.e., have a lower cost-effectiveness ratio). The more expensive pharmacotherapy will be directly assessed to see if the additional cost generates greater effectiveness across the key outcomes of interest. As an alternative approach to examining the full economic impact of this pharmacotherapy, we will estimate the economic benefits associated with reductions in criminal activity and criminal justice system costs, improved employment, and reduced health care use. The difference between economic benefits and intervention costs represents the net economic benefits of the interventions. The primary objectives of the benefit analysis are to identify important economic outcomes for Vivitrol, convert these outcomes into dollar equivalents, and estimate the therapy's total and domain-specific economic benefits. Decreases in some measures between baseline and follow-up, such as number of arrests, represent improvement while other measures, such as hours worked, show improvement with increases. Benefit-cost analysis (BCA) expresses results as a benefit-cost ratio (benefit divided by cost) or a net benefit estimate (benefit minus cost) and considers an intervention costbeneficial if the benefit-cost ratio exceeds unity or if the net benefit estimate is positive. In

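### Employment is never measured, the Crime Grid is not repeated after release and Form 90 shows no visit, so the full net benefit promised in 10.4.3 lacks follow-up data; arrests and incarceration are covered

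*Combined protocol and SAP*

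**What the plan says.** Aim 2 (4.3 Objectives) sets out to test whether Vivitrol, with or without a Patient Navigator, can "reduce drug-related criminal activity, curtail engagement in HIV-risk behaviors, and increase employment compared to a group receiving only drug education". Aim 3, in the same section, will "estimate savings from reduced drug use, reduced criminal activity and re-incarceration, and increased employment". Section 10.4.3 puts these aims into practice and adds health-care use. It will estimate "economic benefits associated with reductions in criminal activity and criminal justice system costs, improved employment, and reduced health care use", convert the outcomes to dollars, and report benefits both overall and domain by domain. It treats employment as a quantity compared from baseline to follow-up: "other measures, such as hours worked, show improvement with increases".

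Section 8.0 says that its measures, together with the DATCAP, supply the economic analysis. In Table 1 the row "CJ-DATS Crime Grid" is marked at screening only, and 8.3.2 says criminal justice history is documented "with this 24-item section of the CJ-DATS intake instrument". Two other crime rows do run after release. Self-reported arrest and treatment history is marked at medical management and assessment visits, and arrest records are marked at assessments. Form 90 is the only entry under Cost. It has no visit marked, and section 8 does not describe it.

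**The concern.** A benefit analysis needs each valued outcome to be recorded after release in every arm and, for a change from baseline, before it as well. If the schedule is followed as printed, the employment comparison in Aim 2 cannot be made. The benefit side of Aim 3 would also be assembled from fewer domains than 10.4.3 lists.

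This matters because 10.4.3 applies a decision rule: the intervention counts as cost-beneficial if the benefit-cost ratio is above one or the net benefit is positive. A figure with domains missing cannot be read against that rule as though it were the total. Net economic benefit is also one of the trial's stated purposes, in the Abstract and again in 5.1. Interview data that are not collected at the visit are hard to recover later, because recall fades and participants are lost.

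**Working it through.** The plan gives no figure to reproduce. The check sets each component named in 10.4.3 against the rows and columns of Table 1 (Screening, Pre-release, Medical Management, and Assessments at months 1, 3, 6, 7 and 12), the instrument descriptions in 8.1 to 8.3, and the outcome lists in 4.3.2, 6.2 and 10.2.

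| Component in 10.4.3 | Baseline source | Post-release source | Result |
|---|---|---|---|
| Criminal justice costs (arrest, conviction, incarceration) | Crime Grid at screening | Self-reported arrest history; arrest records, which under 8.3.1 also cover convictions, sentences and time in custody; secondary outcomes 2 and 5 | Estimable |
| Criminal activity | Crime Grid at screening | Only activity that led to arrest; Crime Grid at 0 post-release visits | Partly estimable |
| Employment, including hours worked | None | 0 Table 1 rows, 0 section 8 instruments, 0 listed outcomes | Not estimable |
| Health-care use | No general measure shown | Drug-treatment history and days (secondary outcome 4), concomitant medications, adverse events; Form 90 with no visit shown | Partly estimable |

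The count is 1 covered, 2 partly covered and 1 not covered.

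Three possible sources for employment were checked:

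- ASI-Lite appears only in the list of abbreviations. It is neither scheduled nor described.
- The DATCAP, as 10.4.3 describes it, collects the resources used to deliver the intervention (staff, buildings, supplies). It does not collect participants' work.
- The Assessments paragraph of the Abstract refers in general terms to further measures of participants' status, but names no employment instrument.

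The consequence can be written as

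net benefit = B(criminal activity) + B(criminal justice) + B(employment) + B(health care) − C.

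The cost term C is collected for the whole intervention through the DATCAP. On the benefit side, B(employment) has no data, B(criminal activity) can rest only on arrests, and B(health care) mainly on drug treatment. The calculation would therefore set full cost against partial benefit. The documents give no dollar values and no expected employment effect, so neither the size nor the direction of the resulting error can be stated.

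The cost-effectiveness half of Aim 3 fares differently. Its example measures in 10.4.3 are re-arrest, abstinent days and time to relapse. Each has post-release data, from the arrest rows, the TLFB or the urine screens.

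**The case against.** The strongest reply is that crime is followed up. Two Table 1 rows record arrests after release, days incarcerated and number of arrests are secondary outcomes, and 10.4.3 itself names re-arrest and number of arrests as measures. This stands. A reader who looks only at the Crime Grid row might infer that crime is measured at screening only, or that three of the four components have no follow-up data. The documents support neither reading. What remains is narrower: 10.4.3 lists criminal activity separately from criminal justice costs, and offending that does not lead to arrest has no post-release source.

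Second, health-care use is named in 10.4.3 and not in the wording of Aims 2 and 3, and it has some follow-up sources. This also stands. Those sources do not add up to a general measure of use.

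Third, blank cells in this table are weak evidence. The text was read from PDF, so a mark in the Form 90 row may have been lost. Table 1 also disagrees with the text elsewhere: the DSM-5 Checklist is marked at screening only, while 8.2.4 has the Checklist or modified CIDI completed at 6 months as well. An Operations Manual (12.1) may hold further detail. The doubt about Form 90 is fair, and the documents do not say what Form 90 contains. The employment gap does not depend on cell marks, because there is no row, no instrument description and no listed outcome.

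Fourth, the primary outcomes are untouched, 10.4.3 presents the benefit analysis as an alternative to cost-effectiveness, and 10.3 describes the trial as preliminary. These points lower the severity but do not supply the missing data.

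**Conclusion.** The point holds in limited form and should be fixed. As written, the plan cannot deliver the Aim 2 comparison on employment or the total net economic benefit of 10.4.3. Employment has no data source at any visit, offending beyond arrest has a baseline but no follow-up, and general health-care use is only partly covered.

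Arrests, convictions and incarceration are measured after release. Their effects, the criminal justice costs and the re-arrest cost-effectiveness ratio can therefore be estimated. It would be wrong to conclude that Aim 3 as a whole fails or that the trial's main result is affected.

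The conclusion on employment and the Crime Grid rests on Table 1 together with the text of section 8, including the description of the Grid as part of an intake instrument. The conclusion on Form 90 is conditional on the row being blank in the source document and on what the form covers.

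**What to change.** 1. **Employment.** Add a brief item, days and hours worked in the past 30 days, at screening, month 6 and month 12. At screening, ask about a window before incarceration, since the preceding 30 days may have been spent in jail. If 30-day values are scaled to a longer period, state that assumption.
2. **Crime Grid.** Repeat it at months 6 and 12 with a since-last-assessment recall window. Count that window from the previous Grid, because the month 7 visit falls between the two.
3. **Form 90.** Confirm or mark its visits in Table 1, describe it in section 8, and state which 10.4.3 domains it supplies. If it already covers employment, item 1 may not be needed.
4. **Otherwise.** Remove each unmeasured domain from Aims 2 and 3 and from 10.4.3. Report net benefit for the measured domains only, labelled as such, and do not read it as a total against the break-even rule.

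The cost is an amendment to Table 1 and the eCRFs and some extra interview time at visits already scheduled. No visit or treatment changes. The fallback needs no new data but narrows what the trial can claim.

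A separate, minor point: secondary outcome (8), "Self-reported motivation for treatment", is listed in 6.2 and 10.2 but has no named measure, and 4.3.2 omits it. Name a measure or delete the outcome.

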11.0 REGULATORY COMPLIANCE AND SAFETY MONITORING

11.1 Regulatory Compliance

This study will be conducted in accordance with the current version of the protocol, in accordance with the ethical principles outlined in the Declaration of Helsinki, consistent with the International Conference on Harmonization Good Clinical Practice (GCP) Guidelines, and all other applicable regulatory requirements.

11.2 Institutional Review Board Approval

Prior to initiating the study, written UCLA and UNM IRB approval will be obtained to conduct the study. Should changes to the study protocol become necessary, protocol amendments will be submitted in writing by the investigators for IRB approval prior to implementation. In addition, the UCLA and UNM IRBs will approve all consent forms, recruitment materials, and any materials given to the participant. Annual reports and progress reports will be submitted to the IRBs annually or as requested.

11.3 Informed Consent

All potential candidates for the study will be given a current local IRB-approved copy of the Informed Consent Form to read in English. Appropriately qualified and trained study personnel will explain all aspects of the study in lay language and answer all of the study candidate's questions. Participants who remain interested after receiving an explanation of the study will be given a short quiz to test his/her understanding of the project, the purpose and procedures involved, and the voluntary nature of his/her participation. Those who cannot successfully answer quiz items will have the study re-explained by research staff with a focus on aspects they did not understand. Anyone who cannot demonstrate appropriate understanding of the study will be ineligible to participate. Those who demonstrate understanding of the study and voluntarily agree to participate will be asked to sign the informed consent form. Participants will not be administered any assessments or study procedures prior to signing informed consent.

The informed consent process is a means of providing study information to each prospective participant and allows for an informed decision about participation in the study. The informed consent form must be updated or revised whenever important new safety information is available, or whenever the protocol is amended in a way that may affect a study participant's consideration for participation in the trial. Every study participant will be given a copy of the signed consent form to keep for reference. Individuals who refuse to participate or who withdraw from the study will be treated without prejudice.

11.4 Drug Accountability

Upon receipt, the investigator, pharmacist, or authorized designee is responsible for maintaining written inventory of the investigational agents. A record of this inventory must be kept and usage must be documented. Any unused or expired investigational agent shall be accounted for.

11.5 Quality Assurance and Safety Monitoring

Protection of the rights and welfare of study participants will be a vigilant process conducted by the research team and by the sponsors of the research. In addition to the data and safety monitoring procedures described in this protocol, additional safety monitoring through the Data and Safety Monitoring Board will be conducted regularly throughout the duration of the study.

11.6 Data and Safety Monitoring Board (DSMB)

This study will utilize a DSMB to oversee ongoing trial progress. The purpose of this board is to determine whether risks emerge during the conduct of the trial that make continuation unethical (e.g., clear and significant superiority of one condition over another). This process is intended to assure the IRBs, the sponsor, and investigators that participants are provided with an accurate and ongoing risk evaluation when participating in research trials. Safety monitoring begins with the initial review of the protocol during the study development process. Reports of participant serious adverse events (SAE) will be provided to the DSMB as they occur. The DSMB will meet as necessary over the study duration.

11.7 Medical Monitor

A Medical Safety Monitor will be responsible for overseeing safety and for evaluating all Adverse Events (AEs). He/She will review all Serious Adverse Events (SAEs) within five days of their occurrence and all other Adverse Events on a regular basis. It is the responsibility of the Principal Investigator to provide this information to the medical safety monitor. It is also the Principal Investigators' responsibility to inform the IRB of any reportable AE/SAE.

11.8 Quality Assurance Monitor

The monitoring of the study will be conducted on a regular basis using a local quality assurance monitor. Investigators will host periodic visits by local QA monitors. The purpose of these visits is to encourage and assess compliance with GCP requirements and to document the integrity of the trial progress.

Monitors will assure that submitted data are accurate and in agreement with source documentation and will also review regulatory/essential documents such as correspondence with the IRB. Areas of particular concern will be participant informed consent, protocol adherence, safety monitoring, IRB reviews and approvals, regulatory documents, participant records, study drug accountability, and Principal Investigator supervision and involvement in the trial. Reports will be prepared following the visit and forwarded to the Principal Investigator.

11.9 Statement of Compliance

This trial will be conducted in compliance with the appropriate protocol, current Good Clinical Practice (GCP), the principles of the Declaration of Helsinki, and all other applicable regulatory requirements.

11.10 Confidentiality

By signing the protocol signature page, the investigators affirm that study information will be maintained in confidence and such information will be divulged to the IRBs, Ethical Review Committee, or similar expert committee; affiliated institution; and employees only under an appropriate understanding of confidentiality with such board or committee, affiliated institution and employees. The lead investigator will obtain a federal Certificate of Confidentiality (CoC), protecting participants against disclosure of sensitive information (e.g., drug use). The Department of Health and Human Services (HHS) office that issues the CoC will be advised of changes in the CoC application information. Confidentiality will be maintained in accordance with all applicable federal regulations and/or state/Commonwealth law and regulations.

Participant records will be kept confidential by the use of study codes for identifying participants on CRFs, secure separate storage of any documents that have participant identifiers, and secure computing procedures for entering and transferring electronic data.

11.11 Health Insurance Portability Accountability Act (HIPAA)

Written authorization from participants for use of protected health information will be obtained. Releases of participant identifying information that are permitted by the HIPAA regulations, but which are prohibited by other applicable federal regulations and/or state/Commonwealth law and regulation, are prohibited.

11.12 Investigator Assurances

UCLA ISAP will maintain a Federal Wide Assurance (FWA) with the HHS Office for Human Research Protection setting forth the commitment of the organization to establish appropriate policies and procedures for the protection of human research subjects. Prior to initiating the study, the Principal Investigator and sub-investigators will sign a protocol signature page, providing assurances that the study will be performed according to the standards stipulated therein.

11.13 Financial Disclosure

All investigators will comply with the requirements of 42 CFR Part 50, Subpart F to ensure that the design, conduct, and reporting of the research will not be biased by any conflicting financial interest. It is the responsibility of the investigator to maintain appropriate disclosure to their individual institution according to their requirements.

